3.2. SCHEDULE OF EVENTS

Schedule of events can be found in table 2 (study flow chart), table 3 (Sub-study 1 of stage 2) and table 4 (Sub-study 2 of stage 2) of the protocol.

3.3. CHANGES FROM PROTOCOL

1. Add modified full analysis set (mFAS) for efficacy endpoints in stage 1 to exclude impact of COVID-19 on week 12 adapted mayo score. For CBP-307CN002 Phase II UC study, approximately 20% missing data is anticipated for the adapted mayo score at Week 12. One major reason is that subjects could not come to site due to COVID-19. mFAS is added to reduce the bias due to those subjects.
2. A Phase II UC study does not have as strict criteria as a pivotal Phase III study. In recent years regulators have been critical of last observation carried forward (LOCF) and similar

Document: Statistical Analysis Plan

Author: [name]

Version Number: 1.1

Version Date: 18Jan2023

Template No.: CS_TP_BS016 Revision 5

Reference: CS_WI_BS005

Effective Date: 01Apr2018

approaches for handling missing data and have advocated using more scientifically justifiable (e.g. multiple imputation methods) in primary analyses of Phase III studies alongside testing assumptions. Recommendation of The Prevention and Treatment of Missing Data in Clinical Trials states, “Single imputation methods like last observation carried forward and baseline observation carried forward should not be used as the primary approach to the treatment of missing data unless the assumptions that underlie them are scientifically justified”. The European Medicines Agency (EMA) Guideline on Missing Data in Confirmatory Clinical Trials states, “The risk of underestimating the variance of treatment effect when imputing can be reduced by proper implementation of techniques such as multiple imputation.”

For CBP-307CN002 Phase II UC study, approximately 20% missing data is anticipated for the adapted mayo score at Week 12. With 20% missing data, the balance in the original FAS population could be lost which could result in biased estimates. Multiple Imputation (MI) can reduce bias arising from missing data.

Therefore, multiple imputation will be used to handle missing data in the analysis of the primary efficacy endpoints at Week 12 for CBP-307CN002 study. The original planned efficacy analysis in the protocol therefore becomes a sensitivity analysis in support of the new primary efficacy analysis, as well as LOCF imputed efficacy analysis.

3. Exploratory clinical remission rate by adapted mayo score is added for clinical discussion as exploratory efficacy endpoint. Exploratory clinical remission rate by adapted mayo score is defined as a rectal bleeding subscore ≤ 1 and a stool frequency subscore ≤ 1 , with an Endoscopy subscore ≤ 1 [excluding friability].
4. 0.2 mg (all stages) analysis is added for a new population to analyse those patients who received 0.2 mg from initial - administration until end of treatment in the study.

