- d. Macular edema: In the preclinical and clinical phase I studies of CBP-307, no eye-related toxicity was observed yet. In this trial, OCT examination will be included. Subjects with macular edema must discontinue the investigational product and undergo examinations including a dilated fundus examination. Every subject whose ophthalmic evaluations reveal abnormalities will be followed until values return to baseline.
- e. Opportunistic infection or severe infection: Tuberculosis, serious bacterial infections, systemic fungal infections, viral infections such as herpes infections (including herpes

- zoster and disseminated herpes simplex) and protozoal infections during the study should be reported as AESI.
- f. Basal cell carcinoma: In a 2-year placebo-controlled clinical study on fingolimod (a similar drug), the incidences of basal cell carcinoma are 2.0% in the group treated with fingolimod 0.5 mg and 0.1% in the placebo control group, respectively. Subjects should be observed for suspected skin lesions, and a specialist assessment should be performed immediately if any suspected skin lesions are noted.
- g. Posterior reversible encephalopathy syndrome and progressive multifocal leukoencephalopathy.

The following steps should be followed:

- a. At every visit, vital signs should be measured in the supine position.
- b. Subjects will be closely monitored in the clinic after their first dose of the initial dose titration regimen for a period of 6 hours after administration. ECGs will be performed predose and at 4 and 6 hours after drug administration, with more frequent assessments as clinically indicated. Vital signs will be measured before administration and at every hour in 6 hours after administration. During titration period, continuous overnight cardiac monitoring should be performed in patients who experience symptomatic bradycardia that requires pharmacologic intervention. In these patients, the first-dose monitoring strategy will continue the following days until the symptoms improve by investigator's assessment, even if the study drug is discontinued. If anyone has prolonged QTc interval during 6-hour observation after dosing, repeated cardiac monitoring in the following days will be conducted until the abnormity improves.

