5. ANALYSIS POPULATION

5.1. STAGE 1 POPULATION

Screened Set (Screened) in stage 1

The screened set will contain all subjects who signed informed consent for stage 1.

Document: Statistical Analysis Plan

Author: [name]

Version Number: 1.1

Version Date: 18Jan2023

Template No.: CS_TP_BS016 Revision 5

Reference: CS_WI_BS005

Effective Date: 01Apr2018

All Randomized Set (Randomized) in stage 1

The randomized set will contain all subjects who are randomized into stage 1, no matter treated or not.

Full Analysis Set (FAS) in stage 1

The full analysis population (FAS) will contain all randomized subjects who receive at least one dose of study medication or placebo in stage 1. FAS will be based on the planned drug taken.

Modified Full Analysis Set (mFAS) in stage 1

The modified full analysis population (mFAS) will contain all randomized subjects who receive at least one dose of study medication or placebo in stage 1 except subjects without week 12 adapted mayo score due to COVID-19. mFAS will be based on the planned drug taken.

Per Protocol Set (PPS) in stage 1

The per-protocol set (PPS) will contain a subset of FAS subjects who do not have major protocol deviation in stage 1.

Definition of major protocol deviation in stage 1:

1. Any Major clinical protocol deviation of Randomization Criteria
2. Any Major clinical protocol deviation of Eligibility and Entry Criteria
3. Any prohibited concomitant medication in clinical protocol deviation
4. IP compliance below 80% or over 120%
5. Have no baseline Adapted Mayo score
6. Have no Week12 Adapted Mayo score
7. Week 12 Adapted Mayo Score is out of visit window
8. Any unblinding during stage 1
9. Any other critical clinical protocol deviations in stage 1

Definition of minor protocol deviation in stage 1:

Clinical protocol deviation except major protocol deviation happened in stage 1.

Document: Statistical Analysis Plan

Author: [name]

Version Number: 1.1

Version Date: 18Jan2023

Template No.: CS_TP_BS016 Revision 5

Reference: CS_WI_BS005

Effective Date: 01Apr2018

Safety Set (SS) in stage 1

The safety set (SS) will contain all randomized subjects who receive at least one dose of study medication or placebo. SS will be based on the actual drug taken.

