8. DISPOSITION AND WITHDRAWALS

Disposition of all screened subjects, Screen failure, screened but not randomized will be

Document: Statistical Analysis Plan

Author: [name]

Version Number: 1.1

Version Date: 18Jan2023

Template No.: CS_TP_BS016 Revision 5

Reference: CS_WI_BS005

Effective Date: 01Apr2018

summarized by count and percentage.

Disposition of all randomized subjects will be tabulated by randomized treatment. The categories will include:

Stage 1:

- All subjects screened
- Screen Failed
- Screen success but not randomized
- All randomized subjects
- Subjects who were randomized but not treated with study medication
- Status of study treatment
 - completed
 - Ongoing
 - Discontinued
- Primary reason for treatment discontinuation
- Entered stage 2

- Study Status
 - Early discontinued in stage 1
 - Stage 1 treatment ongoing
 - Stage 1 post treatment follow-up
 - Completed stage 1 but not entered stage 2
 - Entered stage 2
- Primary reason for study discontinuation

Stage 2:

- Subjects archived clinical response by adapted mayo score (for sub-study 1)/ Subjects not archived clinical response by adapted mayo score (for sub-study 2)

Document: Statistical Analysis Plan

Author: [name]

Version Number: 1.1

Version Date: 18Jan2023

Template No.: CS_TP_BS016 Revision 5

Reference: CS_WI_BS005

Effective Date: 01Apr2018

- All subjects screened
- Status of study treatment
 - Completed
 - Ongoing
 - Discontinued
- Primary reason for treatment discontinuation
- Study Status
 - Early Discontinued in Stage 2
 - Stage 2 Treatment Ongoing
 - Stage 2 Post Treatment Follow-Up
 - Completed
- Primary reason for study discontinuation

Primary reasons for treatment discontinuation, as entered on the eCRF, will be tabulated; the reasons include adverse event, significant protocol deviation, death, non-compliance problems, lost to follow-up, withdrawal by subject, study terminated by sponsor, pregnancy, lack of efficacy or disease progression, or other. COVID-19 will be presented separately after selected from other reasons in 'Other, Specify' category.

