14.2.2. PRIMARY ANALYSIS OF PRIMARY EFFICACY ENDPOINT

The primary efficacy analysis will be based on FAS, mFAS, and PPS.

The covariance (ANCOVA) model with baseline as covariate will be used to analyze the changes in adapted Mayo score from baseline at week 12 between the CBP-307 0.2 mg group and the placebo group stratified by whether the previous treatment with a tumor necrosis factor (TNF)- α antagonist failed (Yes or No). The superiority of the CBP-307 0.2 mg group to placebo on change in adapted Mayo score from baseline at week 12 after treatment will be tested at a significance level of 0.025 with one-sided. If the significance level is reached, then superiority of the CBP-307 0.2 mg will be statistically significant. For subjects enrolled in protocol version 5.0 or earlier in 0.1 mg group, they will be compared with placebo group with same method as 0.2mg QD group, but only results of 0.1 mg group will be presented as supportive results.

The least square mean (LSMEANS), together with the p values and the 95% confidence intervals, between 0.2 mg vs. placebo will be reported using the ANCOVA model (SAS PROC MIXED), with the stratification factor as the confounding factor in the ANCOVA model and the baseline values as covariate.

The change from baseline over time on the Adapted Mayo score will also be plotted by each treatment group for exploratory purpose.

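### The mFAS exclusion for COVID-19 is wider than its site-access reason and can drop illness-related stops from the mFAS response denominators

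*SAP*

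**What the plan says.** SAP 3.3 item 1 adds the mFAS to the populations in the protocol: "Add modified full analysis set (mFAS) for efficacy endpoints in stage 1 to exclude impact of COVID-19 on week 12 adapted mayo score". It notes that "approximately 20% missing data is anticipated for the adapted mayo score at Week 12" and explains: "One major reason is that subjects could not come to site due to COVID-19". The set is meant to reduce bias arising from those subjects.

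SAP 5.1 then defines the mFAS as all randomized, treated stage 1 subjects "except subjects without week 12 adapted mayo score due to COVID-19". Neither section says what counts as due to COVID-19, who decides, or whether the decision is made blind. The FAS in the same section has no such exclusion.

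SAP 14.2.2 states: "The primary efficacy analysis will be based on FAS, mFAS, and PPS". It does not say which of the three sets is decisive. SAP 14.3 and Appendix 2 also list the mFAS for the stage 1 response, remission and mucosal healing endpoints. SAP 14.3.3 names only the FAS and PPS for secondary analyses, so these sections disagree.

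On missing data, SAP 14.3.2 treats a subject with any missing week-12 rating as a non-responder for the binary endpoints. SAP 14.2.3 uses multiple imputation under a missing-at-random assumption for the primary change score.

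**The concern.** A closed site or a travel ban is plausibly unrelated to treatment, and setting those cases aside in a supplementary set is defensible. Stopping because of COVID-19 infection is a different kind of event. It happens after randomization and may depend on the arm. Protocol 3.3.3 describes the drug's expected action as immunosuppressive, and Protocol 7.5 lists as events of special interest "Opportunistic infection or severe infection: Tuberculosis, serious bacterial infections, systemic fungal infections, viral infections such as herpes infections". Protocol 6.2.2 requires withdrawal when dosing stops for more than 7 days (unless for a lymphocyte decrease), so an illness that interrupts dosing that long ends participation.

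The SAP 5.1 wording covers both kinds of loss. If an illness stop has no week-12 score, the mFAS removes what the FAS counts as a failure on the binary endpoints. A set added to reduce bias could then introduce some, and it sits beside the FAS with no ranking between them.

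**Working it through.** **1. Stated reason against stated rule.** SAP 3.3 gives one mechanism: the subject could not come to site. SAP 5.1 tests two things: the week-12 adapted Mayo score is missing, and the cause is COVID-19. A subject who stops because of infection and has no week-12 score meets both tests without meeting the reason. Nothing in SAP 5.1 confines the rule to access.

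**2. Arm size.** SAP 7.4 gives a difference of 1.2, SD 2.0, two-sided alpha 0.05, power 80% and dropout 15%.

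n = 2 × (1.960 + 0.842)² × 2.0² / 1.2² = 43.6, rounded up to 44. Then 44 / 0.85 = 51.8, rounded up to 52. The planned 52 per group reproduces and serves as the FAS denominator below.

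**3. Effect on one arm's response rate.** Let x be responders and k the subjects removed from that arm by the rule, all of them non-responders in the FAS. The FAS rate is x/52 and the mFAS rate is x/(52 − k). Neither x nor k is in the documents; both are assumed.

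| Assumed responders | FAS | mFAS, k=1 | k=2 | k=5 | k=10 |
|---|---|---|---|---|---|
| 20 | 38.5% | 39.2% | 40.0% | 42.6% | 47.6% |
| 26 | 50.0% | 51.0% | 52.0% | 55.3% | 61.9% |

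The k=10 column is an extreme. The anticipated 20% missing from all causes is 0.20 × 52 = 10.4 subjects, so k=10 would make nearly every missing score an illness stop.

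**4. Effect on the treatment difference.** Assume 20 responders of 52 in each arm, so the FAS difference is 0.

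- 2 removed on CBP-307, 0 on placebo: 20/50 − 20/52 = +1.5 points.
- 5 removed on CBP-307, 2 on placebo: 20/47 − 20/50 = +2.6 points.
- 5 removed in each arm: 20/47 − 20/47 = 0.
- 0 removed on CBP-307, 2 on placebo: 20/52 − 20/50 = −1.5 points.

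The sign follows the imbalance in removals.

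**5. Primary endpoint.** For the change in adapted Mayo score, the FAS does not score these subjects as failures; it imputes them from the Mayo items at baseline and week 12. A subject with no week-12 items contributes little outcome information beyond baseline. Removing that subject should therefore move the estimate little. The denominator arithmetic in steps 3 and 4 does not carry over to this endpoint.

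**The case against.** The strongest reply is that the SAP never says illness stops are excluded. SAP 3.3 speaks only of subjects who could not come to site and ties the purpose of the mFAS to them. SAP 8 lists adverse event as its own discontinuation reason and says "COVID-19 will be presented separately after selected from other reasons in" the free-text other category, so an infected subject coded under adverse event might never be flagged as COVID-19. This has force, and it is why the point is that the rule can exclude such subjects, not that it does. It does not settle the matter, because nothing links the disposition coding to the mFAS definition.

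Further objections, and what stands:

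- **An early-termination score may exist.** Protocol 7.2.3.2 and SAP 14.1 schedule the adapted Mayo score at week 12 or early termination. This narrows the affected group, although the SAP does not say whether such a score counts as week 12.
- **The effect falls on exploratory comparisons.** This stands. Protocol 9.8.2.2 and SAP 14.3.3 call the secondary comparisons exploratory, and non-responder imputation applies only to the binary endpoints.
- **The FAS result is reported alongside.** This stands, so a shift would be visible. The sets remain unranked, however.
- **Nothing shows more COVID-19 illness on CBP-307.** This stands. COVID-19 is not named in the special-interest list, and Protocol 3.5 says severe and opportunistic infections were not observed with CBP-307 in earlier trials.

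A reader might infer that the mFAS definitely drops illness stops and so biases efficacy towards the drug, or that the primary result is compromised. The documents support neither. Exclusion of illness stops is only a literal reading of undefined wording, bias towards the drug needs more such stops on CBP-307, and the FAS keeps every one of these subjects.

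**Conclusion.** The concern holds in a limited form. As worded, the SAP 5.1 exclusion is wider than the reason in SAP 3.3 and can remove subjects who stopped because of COVID-19 infection and have no week-12 score. This loss may depend on treatment. The consequence is confined to the mFAS and falls mainly on response, remission and mucosal healing. The effect on the primary change score is probably small, and FAS results do not change.

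Under the assumed counts above, two removals on one arm and none on the other shift the mFAS difference by 1.5 points in either direction, and equal removals with equal responders shift it by nothing. The true size and direction cannot be derived, because the documents give neither the COVID-19 share of the missing scores nor the illness share by arm. The change is still worth making: it narrows a specific rule for a set listed, unranked, beside the FAS and PPS for the primary analysis.

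**What to change.** In SAP 5.1, define the mFAS as the FAS minus subjects whose week-12 adapted Mayo score is missing only for access reasons (site or endoscopy-unit closure, travel or quarantine restrictions) and who have no COVID-19 adverse event leading to discontinuation. Keep illness stops in the mFAS, as non-responders for binary endpoints and in the multiple imputation for change scores. Have the cause of each missing score assigned by reviewers blind to allocation. If stage 1 is already unblinded, document the rule and report mFAS exclusions by cause and arm.

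The drafting cost is about one sentence plus a short review of reasons for missing scores. Two limits apply. A subject can miss the week-12 endoscopy without discontinuing, and the documents do not show that the reason for every missing score was recorded. Blind assignment may also no longer be possible: SAP version 1.1 is dated 18 January 2023, after the planned study end of September 2022. The mFAS would become slightly larger, with possibly less favourable rates.

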4. PLANNED ANALYSES

The following analyses will be performed for this study:

- Analyses for Data Monitoring Committee (DMC) meetings
- Interim Analysis
- Final Analysis

4.1. DATA MONITORING COMMITTEE (DMC)

A DMC SAP, describing the methodology and presentation of results and access to results will be provided by IQVIA as a separate document.

4.2. INTERIM ANALYSIS (PRIMARY ANALYSIS)

One interim analysis (also primary analysis for this study) will take place for this study once all the subjects have completed week 12 (visit 11, last dose/early discontinue visit) in stage 1, the unblind study team will produce the analysis on primary endpoint after database lock. The primary endpoint is to compare clinical efficacy of CBP-307 vs placebo by evaluating the change of adapted Mayo score after 12 consecutive weeks treatment in subjects with moderate to severe UC. Interim analysis will only analyze stage 1 part (including 4-week safety follow-up for early withdrawal subjects). All analysis is used at interim analysis, or week 12.

The interim analysis focuses on efficacy analysis, including change from baseline of adapted Mayo score, complete Mayo score, and IBDQ, and clinical response rate, clinical remission rate, and mucosal healing rate.

The following will be performed in interim analysis:

- Disposition part: patient disposition (details in section 8), major protocol deviation (details in section 8), and analysis sets (details in section 5) summary table in Stage 1 and reference listings.

Document: Statistical Analysis Plan

Author: [name]

Version Number: 1.1

Version Date: 18Jan2023

Template No.: CS_TP_BS016 Revision 5

Reference: CS_WI_BS005

Effective Date: 01Apr2018

- Baseline Characteristics: demographics (details in section 9), medical history (details in section 10), prior medications and procedures (details in section 11) summary table in Stage 1 and reference listings.
- Study Exposure: exposure (details in section 12) and compliance (details in section 13) summary table in Stage 1 and reference listings.
- Efficacy: clinical response rate by adapted mayo score and complete mayo score at week 12; clinical remission rate by adapted mayo score and complete mayo score at week 12; analysis of change in adapted mayo score and complete mayo score from baseline at week 12; mucosal healing rate at week 12; analysis of change in IBDQ score from baseline at week 12 (details in section 14).
- Adverse Events: overall summary table in Stage 1; treatment emergent adverse events (TEAEs), drug-related TEAEs, grade \geq 3 TEAEs, serious TEAEs, TEAEs leading to drug withdrawal, TEAEs leading to death, and TEAEs of special interest by system organ class (SOC) and preferred term (PT) in Stage 1; TEAEs by maximum CTCAE grade, SOC and PT in Stage 1; death details in Stage 1.
- Laboratory: absolute value and change from baseline by visit of hematology, biochemistry, fasting lipids, coagulation, and urinalysis; shift from baseline to worst post-baseline common terminology criteria for adverse events (CTCAE) grade for hematology, biochemistry, fasting lipids, and coagulation; abnormalities in hematology and liver function test. The above summary tables are in Stage 1 as well as their reference listings.
- 12-Lead ECG: absolute value and change from baseline by visit of ECG; shift from baseline to worst post-baseline ECG overall assessment; abnormalities in QT internal and QTcF; shift from baseline to maximum post baseline value and maximum increase from baseline in Stage 1
- Other safety findings: vital signs (VS) part, including absolute value and change from baseline by visit and incidence of markedly abnormal values, and shift from baseline to worst post-baseline overall assessment; pulmonary function test data's absolute value and change

Document: Statistical Analysis Plan

Author: [name]

Version Number: 1.1

Version Date: 18Jan2023

Template No.: CS_TP_BS016 Revision 5

Reference: CS_WI_BS005

Effective Date: 01Apr2018

from baseline; ophthalmologic examination part, including overall assessment by visit and change from baseline; optical coherence tomography part, including overall assessment by visit and change from baseline; dermatologic examination part, including overall assessment by visit and change from baseline in Stage 1.

- Concomitant medications and procedures (details in section 11) in Stage 1.

If a decision is made to perform the primary or main analysis, in order to maintain study integrity with respect to the follow-up visits, safety visits and analyses, a Blind Maintenance Plan will be written. This plan will clearly identify the team (including the statistician) that will perform the primary or main analysis and all related activities, restrict other clinical team members and other Sponsor personnel from access to individual subject treatment allocation and site level analysis results, and ensure that the dedicated team will not participate in the data decisions for the following analyses. However, the dedicated team can participate in the analysis following the final database lock.

